In addition, traditional neuroimaging methods to monitor mental health recovery (e.g. fMRI, PET, EEG) are often impractical in routine care due to cost and limited portability [11-13]. Functional Near-Infrared Spectroscopy (fNIRS) offers a noninvasive, portable, and low-cost brain monitoring tool that can track changes in cerebral blood oxygenation with high temporal resolution [14]. fNIRS has been used successfully to evaluate depression and other mental health conditions by detecting hemodynamic changes in the prefrontal cortex [15, 16]. Applying fNIRS in post-stroke patients could provide an objective biomarker of improvement in depression and cognitive function in response to our intervention [15]. This study is pioneering in Vietnam as it combines physical rehabilitation, MI, and fNIRS-based monitoring to address post-stroke health comprehensively. The knowledge gained may guide future stroke care programs and health policy in resource-limited settings.

Trial Objectives and Hypotheses

Primary Objective: To evaluate the effectiveness of a 6-month multifaceted intervention (Motivational Interviewing plus a home-based rehabilitation program) in improving the mental health (reducing depressive symptoms, fatigue, and cognitive impairment) and physical

functional status of post-stroke patients, compared to standard care alone. The primary endpoints include changes in depression severity, fatigue level, cognitive function, and activities of daily living from baseline to 6 months.

Secondary Objectives: (1) To assess the impact of the intervention on post-stroke quality of life. (2) To explore neurobiological changes associated with depression improvement by measuring prefrontal cortex oxyhemoglobin concentration changes using fNIRS, and determine whether fNIRS biomarkers can serve as predictors of depression status in stroke survivors.

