Hypotheses: We hypothesize that stroke survivors receiving the combined MI and home-based rehabilitation intervention will show significantly greater improvements in mental health outcomes (lower Patient Health Questionnaire-9 depression scores and Fatigue Severity Scale scores, improved Mini-Mental State Examination scores) and physical function (higher Barthel Index scores) over 6 months, compared to those receiving standard care. We also hypothesize that the intervention group will exhibit measurable increases in prefrontal cortical activation (oxyhemoglobin levels) on fNIRS correlating with reduction in depressive symptoms, and that specific fNIRS-derived metrics will predict depression remission status with reasonable accuracy.

Study Design

This study is a single-center, parallel-group randomized controlled trial with a 1:1 allocation ratio to intervention versus control. The trial was conducted at the Vietnam National Geriatric Hospital from 2021 to 2022. A total of 92 stroke survivor participants were enrolled and randomly assigned to either the Intervention group, which received a multi-component program (Motivational Interviewing plus a home-based rehabilitation regimen), or the Control group, which received standard care and general health advice. The study duration for each participant is approximately 6 months, with assessments at baseline and follow-up at 1, 3, and 6 months post-enrollment. Figure 1 presents the planned participant flow per CONSORT guidelines (see Schedule of Events below for timeline of activities). The trial is open-label: due to the nature of the interventions, neither participants nor intervention providers were blinded to group assignment. To reduce potential bias, outcome assessments were standardized, and the data analyst/statistician remained blinded to group labels during analysis.

Eligibility Criteria

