(e.g. left orbitofrontal cortex, ventrolateral PFC) and how these values change from pre- to post-intervention. Prior studies suggest that greater increases in prefrontal HbO₂ activation correspond to better emotional and cognitive outcomes [26]. We will explore whether our intervention group shows increased HbO₂ responses over time relative to controls, and whether certain threshold values of HbO₂ change can distinguish participants with resolved depression from those with persistent depression by 6 months. These **fNIRS measurements** are considered an exploratory outcome and will not be used as primary endpoints, but rather to supplement and biologically contextualize the clinical findings.

All outcome instruments (questionnaires and cognitive tests) are administered in the Vietnamese language by research staff. Standardized, validated Vietnamese versions are used for all scales (e.g. the PHQ-9 and MMSE have validated translations). For quality control, the same instruments are used at each follow-up, and staff members were trained to maintain consistency in administration.

Schedule of Events (Study Timeline)

The schedule of enrollment, interventions, and assessments is based on SPIRIT guidelines and is summarized below:

- **Screening & Baseline (Month 0):** Potential participants are screened against inclusion/exclusion criteria and provide written informed consent. At enrollment (pre-intervention baseline), we collect demographic information and stroke history (including stroke type, time since onset, lesion location, disability status by Modified Rankin Scale, etc.). Baseline assessments include the PHQ-9, FSS, MMSE, Barthel Index, and SIS administered via interview, as well as the first fNIRS measurement during a cognitive task. After baseline assessments, participants are randomized to either the intervention or control group. For those in the intervention arm, the first MI session typically occurs immediately or within a week after randomization, and the home-based rehab program is initiated with a visit scheduling within the first week.

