### 3. Outcomes and Endpoint Definitions

#### Primary Efficacy Outcomes:

- **Depression Severity:** Change in Patient Health Questionnaire-9 (PHQ-9) score from baseline to follow-ups. The PHQ-9 is a 9-item scale (0–27 range); higher scores indicate worse depressive symptoms. The primary comparison will be the difference in mean PHQ-9 change from baseline to 6 months between groups. Additionally, trajectories over all time points will be considered. We will also examine the proportion of participants in each group achieving remission of depression (PHQ-9 < 5, for example) at 6 months as a supportive outcome.

- **Fatigue Level:** Change in Fatigue Severity Scale (FSS) score (range 9–63, higher = more fatigue). Same approach as PHQ-9: continuous score change and possibly categorization (e.g., FSS  $\geq 36$  indicating significant fatigue) for supplementary analysis.

- **Cognitive Function:** Change in Mini-Mental State Examination (MMSE) score (0–30, higher = better cognitive function). We will consider the mean change and group differences; additionally, the proportion of participants with cognitive impairment (MMSE  $\leq 24$ ) at each time point will be noted.

- **Physical Functional Independence:** Change in Barthel Index (BI) score (0–100, higher = more independent). Primary focus on mean score change at 6 months. Also, we may categorize outcomes (e.g., BI  $\geq 90$  as independent vs <90) for descriptive comparison.

Each of these primary outcomes will be analyzed as a continuous variable using appropriate parametric or nonparametric methods as outlined in Section 4. The primary time horizon for efficacy is the 6-month post-intervention assessment, though intermediate time points will be analyzed to observe trends.

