#### Secondary Outcomes:

- **Quality of Life:** Stroke Impact Scale (SIS) 3.0 overall score (0–100, higher = better). Change in SIS from baseline to 6 months will be compared between groups. SIS subdomains (physical, emotion, communication, etc.) might also be explored for additional insights, but the overall score is the main focus.

- **Functional Near-Infrared Spectroscopy (fNIRS) Biomarkers:** Several exploratory endpoints derive from fNIRS measurements of cortical hemodynamics during a cognitive task:

- Mean or peak change in oxyhemoglobin ( $\Delta\text{HbO}_2$ , measured in  $\text{mmol}\cdot\text{mm}$  or arbitrary units) in predefined regions of interest (e.g., left orbitofrontal cortex, right orbitofrontal cortex, dorsolateral prefrontal cortex) at baseline, 3 months, and 6 months.
- The change in  $\Delta\text{HbO}_2$  from baseline to 6 months for those regions.

- We will specifically evaluate if the intervention group shows a greater increase in  $\Delta\text{HbO}_2$  in the left orbitofrontal cortex over time compared to controls, as prior evidence suggested a link between orbitofrontal activation and depression improvement.

- **Derived binary outcomes for ROC analysis:** e.g., “6-month depression status” (yes/no based on PHQ-9 threshold as noted) and using fNIRS metrics (such as 6-month  $\Delta\text{HbO}_2$ ) as predictors.

- **Other Clinical Measures:** If collected, the Modified Rankin Scale (mRS) for disability and NIH Stroke Scale (NIHSS) at baseline will be described but not tested as outcomes. The trial registration did not include these as outcomes, but baseline differences will be accounted for if necessary.

**Safety Outcomes:** The study will note any adverse events (AEs) or serious adverse events (SAEs) reported during the 6-month period, such as falls, medical complications, or psychological distress. Given the nature of the intervention, we do not anticipate intervention-related SAEs. AEs will be coded and summarized by group (e.g., number of falls during follow-up, any hospitalizations, etc.). No formal hypothesis testing on safety outcomes is planned due to expected low incidence and lack of power for such events.

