#### 4.5 fNIRS Data Analysis

The fNIRS data will undergo preprocessing (performed in MATLAB) including filtering (to remove noise and drift), motion artifact correction, and segmentation of the task period. For each participant and each session (baseline, 3m, 6m), we will derive summary metrics such as the average oxyhemoglobin concentration change ( $\Delta[\text{HbO}_2]$ ) in specific regions of interest during the cognitive task relative to rest baseline. We might average signals over channels covering the left orbitofrontal cortex (OFC), right OFC, ventrolateral PFC, etc., based on the sensor layout. These ROI-level  $\Delta\text{HbO}_2$  will be the variables used for analysis.

**Longitudinal ROI Analysis:** Using GEE, we will model  $\Delta\text{HbO}_2$  as the outcome with group, time (0, 3, 6 months), and group $\times$ time as factors, similar to other outcomes. We anticipate, for instance, a significant group $\times$ time effect in left OFC  $\text{HbO}_2$ , indicating the intervention group's  $\text{HbO}_2$  increases over time relative to control (as observed in preliminary analyses). If GEE shows significance, we will follow up with post-hoc tests of group differences at 3 and 6 months, and time differences within each group. If data are normally distributed and complete, an LMM could also be used for confirmation. If some fNIRS measurements are missing (due to technical issues or dropouts), GEE can handle missing under MAR assumptions.

**Correlation with Clinical Outcomes:** We will compute Pearson or Spearman correlations between changes in fNIRS metrics (e.g.,  $\Delta\text{HbO}_2$  from baseline to 6m in a region) and changes in clinical scores (e.g., PHQ-9 drop) across individuals. A positive correlation would indicate that participants with larger brain activation increases tended to have greater depression improvement, supporting fNIRS as a biomarker. A small p-value would suggest significance of this correlation.

**ROC Analysis:** One key exploratory analysis is to evaluate whether fNIRS measures can classify depression status. We will define a binary variable for depression at 6 months (for

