example, PHQ-9  $\geq 10$  indicating clinically significant depressive symptoms vs  $< 10$  indicating minimal symptoms). We will then take certain fNIRS measures (like the 6-month left OFC HbO2 level or the change in that level from baseline) and perform ROC curve analysis. The area under the ROC curve (AUC) will be calculated to assess discrimination ability. If AUC is significantly above 0.5, it indicates some predictive value. We will identify the optimal cutoff on the fNIRS measure that maximizes Youden's J (sensitivity + specificity - 1). For that cutoff, we will report sensitivity, specificity, positive predictive value, and negative predictive value. To account for sample variability, we will use a bootstrap approach (e.g., 1000 bootstrap samples of the data) to derive a confidence interval for the AUC and for the sensitivity/specificity at the chosen cutoff. For example, in preliminary findings, a cutoff  $\Delta$ HbO2 of approximately -0.47 mmol·mm in left OFC was identified for the experimental group depression prediction; we will verify if similar thresholds emerge and their stability via bootstrapping. This analysis is exploratory and aimed at generating hypotheses for future larger studies on using fNIRS as a screening tool.

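### The fNIRS ROC in SAP 4.5 classifies patients by 6-month PHQ-9 alone, so it addresses current depression status but not the protocol's questions on remission and on resolved versus persistent depression

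*SAP*

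**What the plan says.** The protocol states the fNIRS aim in three ways.

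- Secondary objective 2 (Trial Objectives and Hypotheses) is to "determine whether fNIRS biomarkers can serve as predictors of depression status in stroke survivors".
- The Hypotheses paragraph expects that "specific fNIRS-derived metrics will predict depression remission status with reasonable accuracy".
- Outcome Measures (Neuroimaging Biomarkers) asks whether threshold values of HbO2 change "can distinguish participants with resolved depression from those with persistent depression by 6 months".

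The SAP turns these into one ROC analysis. Section 4.5 says "We will define a binary variable for depression at 6 months". Its example is a PHQ-9 of 10 or more, "indicating clinically significant depressive symptoms vs" a score below 10. The candidate predictors are the 6-month left orbitofrontal HbO2 level "or the change in that level from baseline". SAP section 3 lists the same outcome as 6-month depression status, "yes/no based on PHQ-9 threshold as noted", and separately mentions "remission of depression (PHQ-9 < 5, for example) at 6 months" as a supportive outcome for comparing the arms. None of these definitions refers to baseline PHQ-9, and no analysis set is named for the ROC.

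The protocol's Eligibility Criteria exclude psychiatric illness diagnosed before the stroke. They neither require depression after the stroke nor set a minimum PHQ-9. Baseline PHQ-9 and baseline fNIRS are both collected (Schedule of Events).

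**The concern.** Remission, resolved and persistent all describe people who were depressed earlier. Current depression status does not. The SAP's outcome is of the second kind, and two of the three protocol statements are of the first.

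With no entry threshold, the 6-month split sorts four kinds of patient into two classes. Resolved and never-depressed patients fall below the cut-off; persistent and new-onset cases fall at or above it. Moving the cut-off from 10 to 5 changes who counts as depressed but leaves the mixing in place. It matters most when the predictor is HbO2 change, because a never-depressed patient has no recovery for that change to track.

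Section 4.5 commits to an AUC, a Youden cut-off, sensitivity, specificity and predictive values, and presents them as input to larger studies. If they are read as evidence about remission, they could mislead either way: a marker that follows recovery may look weak, and one that does not may look useful.

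**Working it through.** **The plan's own figures.** The documents give no sample size, expected AUC or depression rate for the ROC. The only sample-size figure is for mean PHQ-9 change: 2 × [5.5 × (1.960 + 0.842) / 3.43]² = 40.4, so 41 per group against the stated 43, which is close enough. It has no bearing on the ROC beyond fixing N at 92.

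**Does another analysis answer the question?**

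- The correlation in SAP 4.5 relates HbO2 change to PHQ-9 change across all individuals. It uses baseline PHQ-9 but does not classify patients as resolved or persistent.
- The remission comparison (SAP 3 and 4.4) is between arms and does not involve fNIRS.
- The preliminary cut-off in SAP 4.5 refers to the experimental group. Restricting by arm would not remove never-depressed patients.

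So no planned analysis makes the resolved-versus-persistent classification.

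**Size of the mixing.** All inputs here are assumptions: 30%, 40% or 50% of the 92 depressed at baseline, half of those resolved at 6 months, 5% new onset among the rest, no missing data.

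| Depressed at baseline | Persistent | New onset | Resolved | Never depressed | Resolved share of non-depressed class (w) |
|---|---|---|---|---|---|
| 30% | 13.8 | 3.2 | 13.8 | 61.2 | 13.8/75.0 = 0.184 |
| 40% | 18.4 | 2.8 | 18.4 | 52.4 | 18.4/70.8 = 0.260 |
| 50% | 23.0 | 2.3 | 23.0 | 43.7 | 23.0/66.7 = 0.345 |

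Never-depressed patients would make up 66% to 82% of the non-depressed class.

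**Pooled AUC.** If new-onset cases have the same marker distribution as persistent ones, then

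AUC(pooled) = w × AUC(resolved vs cases) + (1 − w) × AUC(never depressed vs cases).

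*HbO2 change as predictor.* Assume resolved cases exceed persistent cases by 0.8 SD. The remission AUC is Φ(0.8/√2) = 0.714.

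- Never-depressed patients show no change (their AUC is 0.5): the pooled AUC is 0.5 + 0.214w, which is 0.539, 0.556 and 0.574 at 30%, 40% and 50%.
- They show half the resolved group's change, so their AUC is Φ(0.4/√2) = 0.611: the pooled AUC is 0.630, 0.638 and 0.647.
- They change as much as the resolved: the pooled AUC is 0.714, so the two coincide.

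*6-month level as predictor.* Assume no ability to separate resolved from persistent (AUC 0.50), but AUC 0.80 for never-depressed patients against cases. The pooled AUC is 0.5w + 0.8(1 − w), which is 0.745, 0.722 and 0.697.

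**Power against AUC 0.5** (simulation, Mann-Whitney test, 40% depressed at baseline, 0.8 SD). With no change in the never-depressed, power is about 11% pooled and 61% restricted to the baseline-depressed. With never-depressed change at 75% of the resolved group's, it is about 70% pooled and 63% restricted. The ranking therefore turns on a quantity the documents do not give.

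**Precision of a restricted ROC.** The Hanley-McNeil standard error at AUC 0.70 is 0.101 with 13.8 patients per class and 0.078 with 23 per class. The 95% half-widths are about 1.96 × 0.101 = 0.20 and 1.96 × 0.078 = 0.15.

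**The case against.** The strongest reply is that the all-participant ROC is right for what the SAP says it is doing. Secondary objective 2 concerns depression status in stroke survivors, and section 4.5 gives the eventual use as screening. For screening, never-depressed patients belong in the negative class. This stands. A reader might infer that secondary objective 2 goes unanswered, but its wording requires no earlier depression, so the documents do not support that.

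Second, both documents call the fNIRS work exploratory, and section 4.5 describes the ROC as hypothesis-generating. This also stands, and no efficacy conclusion depends on it. It limits the weight of the point but does not remove the mismatch, because a reported cut-off with sensitivity and specificity still needs a defined population.

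Third, the correlation analysis would give a remission-tracking signal another chance to show. That is fair, though it is not the classification the protocol asks for.

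Fourth, a reader might infer that pooling always hides a real biomarker, or that the restricted set always has more power. Neither follows. The level-marker case shows inflation, and pooled power is higher once never-depressed patients show most of the resolved group's change. The protocol does not exclude such change: it expects HbO2 to rise in the intervention group without conditioning on baseline depression.

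**Conclusion.** The mismatch holds on the text alone. As written, the SAP's ROC tests current depression status at 6 months and leaves two protocol statements untested: the resolved-versus-persistent question and the remission hypothesis.

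The numerical consequence is conditional. The documents give no baseline depression rate, resolution rate, new-onset rate or HbO2 effect, so the figures show what is possible and are not forecasts. Within the range tried, the pooled AUC can fall well below the remission AUC, equal it, or suggest discrimination where there is none for remission. The all-participant AUC is therefore not evidence for or against prediction of remission.

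This is a cheap improvement to one exploratory analysis. The primary outcome analyses are unaffected.

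**What to change.** In SAP section 4.5:

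1. Keep the all-participant ROC and label it as current depression status at 6 months.
2. Add an exploratory remission ROC, resolved versus persistent, with baseline-to-6-month HbO2 change as predictor. Restrict it to participants whose baseline PHQ-9 is at or above the same cut-off used at 6 months, and fix that cut-off in advance.
3. Report the four counts from crossing baseline with 6-month status: persistent, resolved, new onset, never depressed.
4. State that the all-participant AUC will not be interpreted as bearing on remission.

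The cost is a few sentences and one further run on data already collected. The drawback is precision. With 30% to 50% depressed at baseline (an assumption), the remission ROC would use about 28 to 46 of the 92 patients, some 14 to 23 per class if half resolve. Its Youden cut-off, sensitivity and specificity would be unstable and should be shown with their bootstrap intervals, which will be wide.

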These four measures (PHQ-9, FSS, MMSE, and Barthel Index) are considered the primary outcomes, representing mental and physical health domains targeted by the intervention. In addition, we track a secondary outcome of overall post-stroke recovery:

- **Quality of Life:** Evaluated using the **Stroke Impact Scale 3.0 (SIS-16)**, a stroke-specific quality-of-life questionnaire [24]. The SIS assesses 8 domains including strength, hand function, mobility, ADL/IADL, memory, communication, emotion, and social participation. Domain scores and an overall composite can be calculated on a 0–100 scale, with higher scores indicating better functioning and quality of life [24]. We will primarily use the total SIS score as an outcome of global recovery. (This measure is secondary/exploratory; not all participants may complete the full SIS due to time constraints.)
- **Neuroimaging Biomarkers (Exploratory):** Changes in cerebral oxyhemoglobin concentration in the prefrontal cortex, as measured by fNIRS, serve as an exploratory biomarker of depression and cognitive improvement. A portable 48-channel fNIRS device (NIRSIT, OBELAB, South Korea) is used to record cortical hemodynamic responses while participants perform a brief cognitive task (e.g. verbal fluency task) at baseline, 3 months, and 6 months (fNIRS is not administered at the 1-month visit). The fNIRS optode array is positioned over the forehead (frontopolar and lateral prefrontal regions) to capture activity in brain areas implicated in mood regulation (such as the orbitofrontal cortex). Oxyhemoglobin (HbO_2) and deoxyhemoglobin signals are calculated using the modified Beer–Lambert law and are sampled at high temporal resolution during the cognitive challenge [25]. For analysis, we will examine the mean change in HbO_2 from baseline during task performance for specific regions of interest

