- **Intervention Period (Month 0 to Month 6):** The intervention group undergoes the structured program as described: MI sessions weekly in Month 1 and biweekly in Months 2–3 (8 sessions total), and physical therapist home visits weekly in Months 1–2, biweekly in Months 3–4, and monthly in Months 5–6. All intervention activities are logged. The control group receives no intervention during this period beyond usual care, though both groups continue to attend routine medical appointments as scheduled.
- **1-Month Follow-up (Month 1):** Both groups return for a follow-up visit at ~1 month post-baseline. Outcome assessments at this visit include PHQ-9, FSS, MMSE, Barthel Index, and SIS. These are administered by the study assessor to track early changes. (No fNIRS measurement is performed at 1 month in this study design.) The intervention group will have completed roughly four MI sessions by this point (if on schedule) and continues with weekly rehab visits through Month 2. The control group's visit consists of their routine check-up and outcome questionnaires.
- **3-Month Follow-up (Month 3):** A mid-point evaluation is conducted at 3 months for all participants. Outcome measures (PHQ-9, FSS, MMSE, Barthel, SIS) are administered again, and the **second fNIRS** assessment is performed for both groups under the same protocol as baseline. By Month 3, participants in the intervention arm will have completed the course of eight MI sessions (the final MI sessions occur around

week 10–12). They will also have had biweekly rehab visits through Month 3. The 3-month follow-up allows assessment of mid-intervention improvements and provides data for any necessary intervention adjustments. Control group participants continue to receive standard care and are assessed in parallel.

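### The fNIRS aim is worded as prediction, but every ROC predictor the SAP names needs the month-6 scan taken at the visit that defines the outcome

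*SAP*

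**What the plan says.** **Aim.** Under Trial Objectives and Hypotheses, the protocol's second secondary objective includes to "determine whether fNIRS biomarkers can serve as predictors of depression status in stroke survivors". The Hypotheses paragraph adds that "specific fNIRS-derived metrics will predict depression remission status with reasonable accuracy".

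**Outcome of the ROC.** SAP Section 4.5 will "evaluate whether fNIRS measures can classify depression status. We will define a binary variable for depression at 6 months". Its example of the split is PHQ-9 of 10 or more against below 10.

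**Predictors in the ROC.** The same section continues: "We will then take certain fNIRS measures (like the 6-month left OFC" HbO2 "level or the change in that level from baseline) and perform ROC curve analysis". SAP Section 3, Secondary Outcomes, describes the 6-month depression status as "yes/no based on PHQ-9 threshold as noted) and using fNIRS metrics (such as 6-month" ΔHbO2) as predictors.

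**Reading of the result.** Section 4.5 takes an AUC significantly above 0.5 as showing some ability to predict. It uses prediction wording again for a cut-off from preliminary findings. It also calls the analysis exploratory and points to later work on screening.

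**Scan times.** The protocol's Outcome Measures section schedules fNIRS "at baseline, 3 months, and 6 months (fNIRS is not administered at the 1-month visit"). The Schedule of Events says of the 3-month scan that the "assessment is performed for both groups under the same protocol as baseline". It places the final scan and the final PHQ-9 together at the month-6 evaluation.

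**The concern.** A claim that a marker predicts depression status is normally understood to mean that it is measured before the status is known. If marker and status are measured at the same visit, the AUC describes how well the marker reflects current state. A good concurrent AUC may mean only that brain activation and mood move together at month 6. It does not show that a scan taken earlier would identify who will be depressed, or who will have recovered, at month 6.

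What is at stake is the conclusion on a stated secondary objective and hypothesis. If the analysis is run with the predictors named and read as the SAP says, a concurrent AUC would be reported as evidence of prediction. The scans that could address prediction would not have been used for it.

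A related gap concerns the outcome. The hypothesis is about remission, whereas the ROC example is about being at or above a depression cut-off. The documents do not settle which status is meant, or in whom remission is assessed.

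**Working it through.** The documents give no sample size, power or target AUC for the ROC analysis, so there is no planned figure to reproduce. The check is one of timing.

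**1. Lead time = month of outcome minus month at which the predictor is first available.** The outcome is PHQ-9 status at month 6 (SAP 4.5).

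| Predictor | Named in the SAP for the ROC? | First available | Lead time |
|---|---|---|---|
| 6-month left OFC HbO2 | Yes (Sections 3 and 4.5, as an example) | Month 6 | 6 − 6 = 0 months |
| Change in that level from baseline | Yes (Section 4.5, as an example) | Month 6 | 6 − 6 = 0 months |
| Baseline scan alone | No | Month 0 | 6 − 0 = 6 months |
| 3-month value, or 0-to-3-month change | No | Month 3 | 6 − 3 = 3 months |

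The change score uses the baseline scan but cannot be computed until the month-6 scan exists. The correlation analysis in Section 4.5 does not fill the gap: its example pairs fNIRS change from baseline to 6 months with change in clinical scores.

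**2. Can a concurrent AUC stand in for an earlier one?** This is an illustration on assumed values that are not in the documents. Let D be 6-month depression (standard normal), F6 = r·D + √(1 − r²)·e₁ the 6-month scan, and F0 = ρ·F6 + √(1 − ρ²)·e₂ the earlier scan, with independent standard normal errors. The earlier scan is thus related to the outcome only through the 6-month scan. A participant is depressed if D lies in the top 20%, 35% or 50%. With r from 0.3 to 0.5, ρ from 0.3 to 0.7 and 400,000 simulated participants per scenario:

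| Predictor | AUC over all scenarios |
|---|---|
| 6-month level | 0.64 to 0.75 |
| Change from baseline to 6 months | 0.55 to 0.65 |
| Baseline scan | 0.54 to 0.67 |

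At 35% prevalence and r = 0.5, the 6-month AUC is about 0.73 to 0.74 whatever ρ is. The baseline-scan AUC runs from 0.57 (ρ = 0.3) to 0.66 (ρ = 0.7). So the concurrent AUC does not reveal the earlier one.

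**3. Precision at N = 92.** The Hanley-McNeil variance is [A(1 − A) + (n₁ − 1)(a − A²) + (n₀ − 1)(b − A²)] / (n₁n₀), with a = A/(2 − A) and b = 2A²/(1 + A). At an assumed prevalence of 35%, n₁ = 32 and n₀ = 60. For A = 0.6, a = 0.429 and b = 0.450, so the variance is (0.24 + 31 × 0.0686 + 59 × 0.09)/1920 = 7.68/1920 = 0.0040. The SE is 0.063 and the 95% half-width 1.96 × 0.063 = 0.12. For A from 0.5 to 0.7 and prevalence from 20% to 50%, the half-width is about 0.11 to 0.15.

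**4. The outcome definition.** SAP Section 3 refers back to a PHQ-9 threshold already given. The only earlier one in that section is remission, PHQ-9 below 5, offered as an example. Section 4.5 offers 10 or more against below 10, also as an example. A participant scoring 5 to 9 at month 6 is not in remission under the first and not depressed under the second. The documents give no count of such participants. Eligibility sets no PHQ-9 entry threshold, so someone never depressed could score below 5 at month 6 and be counted as remitted.

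**The case against.** The strongest reply is that the documents do not require forecasting. The objective and hypothesis state no lead time. The protocol's Outcome Measures section asks whether thresholds of HbO2 change can separate participants whose depression has resolved from those in whom it persists by 6 months. The SAP's change-from-baseline example does this. The SAP also speaks of classifying, discrimination and screening, and the protocol presents fNIRS partly as a way to monitor recovery. The analysis is exploratory, and fNIRS is expressly not a primary endpoint.

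Much of this stands. Concurrent classification is a legitimate aim and should be kept. A reader might infer that the wrong analysis was planned; the documents do not support that.

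A reader might also infer that prediction has been ruled out. That goes too far. The predictors are introduced as examples, and Section 4.5 derives region-level metrics for every session, so an earlier scan could be used. The accurate statement is that none is named.

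Nor do the documents show one fixed remission rule being replaced by another. Both cut-offs are illustrative, and the hypothesis gives none. The fault is under-specification.

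What the reply does not remove is the mismatch between the prediction wording, including the SAP's reading of the AUC, and predictors that exist only at the outcome visit.

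**Conclusion.** The point holds as a minor one. With the predictors the SAP names, the ROC measures concurrent classification, with a lead time of 0 months against the 3 or 6 months the scan schedule allows. It can show whether fNIRS reflects depression status at month 6. It cannot show that fNIRS predicts later status or remission. No primary endpoint or primary conclusion is affected.

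The timing rests on the documents alone. The AUC ranges rest on assumed correlations and prevalences and on a simple model. They show that a concurrent AUC is a poor guide to an earlier one, not what this trial will find. The half-widths assume all 92 participants have usable scans. The number whose class depends on the choice of cut-off is unknown.

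**What to change.** - **Label.** Keep the month-6 ROC, call it concurrent classification, and drop the prediction wording for it in SAP Sections 3 and 4.5.
- **Add earlier predictors.** For the prediction hypothesis, name baseline left OFC HbO2, and the 3-month value or the 0-to-3-month change, as predictors of 6-month status.
- **Use a fair comparator.** Report discrimination beyond treatment arm and the PHQ-9 available when the scan was taken: baseline PHQ-9 for the baseline scan, baseline and 3-month PHQ-9 for the 3-month scan. Comparing a 3-month scan with baseline PHQ-9 alone would credit fNIRS with information that may come only from its later date. Omitting arm could let the scan stand in for allocation. Give confidence intervals and mark the results exploratory.
- **Settle the outcome.** Use one 6-month status definition throughout SAP Sections 3 and 4.5. Assess remission, as resolved against persistent depression, only in participants depressed at baseline.

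**Cost.** This changes SAP wording and adds a few exploratory models. The scans and PHQ-9 assessments are already scheduled, so no new data are needed. AUCs from earlier scans will probably be lower, and any gain over PHQ-9 will be imprecise. Restricting to participants depressed at baseline widens the intervals further, since width scales roughly with 1/√N. If half the sample qualified (an assumption), they would be about √2 = 1.4 times as wide.
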